## **9.5.2. Efficacy Analyses for the Sub-Study Population**

### **9.5.2.1. Primary Efficacy Analysis**

The primary efficacy variables will be analyzed using a multiple imputation approach with mixed-effect model for repeated measure (MMRM) based on the FAS with adjustment for missing data due to treatment discontinuation for the reasons of lack of efficacy or AEs assuming the WOMAC scores would on average return to baseline values. The missing data for patients who discontinued treatment due to lack of efficacy or AEs will be imputed with values centered at the mean baseline value of the treatment group that patients were randomized to. Missing data will be imputed 50 times to generate 50 complete data sets. Each imputed data set will be analyzed using the MMRM with terms for baseline score corresponding to the primary efficacy variable (eg, WOMAC pain subscale score at baseline for the analysis of change from baseline in WOMAC pain subscale score), treatment, randomization strata, visit, and treatment-by-visit interaction. The MMRM will be performed using the MIXED procedure in the Statistical Analysis System (SAS) with an unstructured covariance matrix to model the within-patient errors. Denominator degrees of freedom will be estimated using Kenward-Roger's approximation. The results from the 50 analyses will be combined using Rubin's formulae (PROC MIANALYZE). The least-squares means estimates for the mean change from baseline to week 16, as well as the difference of the estimates between fasinumab and placebo, with the corresponding standard error, p-value and associated 95% confidence interval will be provided. Hypothesis testing will be performed as specified in Section 9.1 to control for multiplicity. Data collected after discontinuing treatment up to week 16 will not be used in the primary efficacy analysis, but used in a treatment policy sensitivity analysis

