- H₂₃: There is no treatment difference between fasinumab 1 mg Q8W and placebo in the proportion of patients with $\geq 30\%$ improvement in the WOMAC pain subscale scores at week 16 versus there is a treatment difference in proportion of patients with $\geq 30\%$ improvement in WOMAC pain at week 16

The estimand for the primary efficacy objective is the difference in means between each fasinumab dose+protocol-defined rescue medication and placebo+protocol-defined rescue medication in the change from baseline to week 16 in the WOMAC pain and physical function scores in the FAS-substudy, regardless of whether or not prohibited medication had been taken. Data collected after discontinuing treatment up to week 16 will not be used in the primary efficacy analysis but used in a treatment policy sensitivity analysis. The missing data for patients who discontinued treatment due to lack of efficacy or AEs will be imputed with values centered at the mean baseline value of the treatment group that patients were randomized to. The missing data for patients discontinued treatment due to other reasons will be imputed under missing-at-random assumption using the regression method with adjustment for covariates including treatment group, randomization strata, and baseline score. Intermittently missing data will be imputed using Markov Chain Monte Carlo method.

The primary efficacy variables will be analyzed using a multiple imputation approach with mixed-effect model for repeated measure (MMRM) based on the FAS-substudy with adjustment for missing data due to treatment discontinuation for the reasons of lack of efficacy or AEs assuming the WOMAC scores would on average return to baseline values. Missing data up to week 16 will be imputed 50 times to generate 50 complete data sets by using the SAS procedure PROC MI following the 3 steps below:

- Step 1: The monotone missing pattern is induced by Markov Chain Monte Carlo (MCMC) method in MI procedure using seed number [REDACTED]
- Step 2: The missing data at subsequent visits will be imputed using the regression method for the monotone pattern with seed number [REDACTED] and adjustment for covariates including treatment groups, randomization strata, relevant baseline and all values at preceding visits.

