- Step 3: The initially missing and now imputed data for patients discontinued from the study treatment due to lack of efficacy or AEs will be adjusted to be centered at the mean baseline value for that treatment group, i.e., final imputed score = imputed score under MAR - (mean change from baseline score at the post-baseline time point for the treatment group based on patients on treatment with non-missing data at that time point).

Each imputed data set will be analyzed using the MMRM with terms for baseline score corresponding to the primary efficacy variable (e.g. WOMAC pain subscale score at baseline for the analysis of change from baseline in WOMAC pain subscale score), treatment, randomization strata, visit, and treatment by visit interaction. The MMRM will be performed using the MIXED procedure in the Statistical Analysis System (SAS) with an unstructured covariance matrix to model the within-patient errors. Denominator degrees of freedom will be estimated using Kenward-Roger's approximation.

- The results from the 50 analyses will be combined using Rubin's formulae (PROC MIANALYZE). The least squares mean estimates for the mean change from baseline to week 16, as well as the difference of the estimates between fasinumab and placebo, with the corresponding standard error, p-value and associated 95% confidence interval will be provided.

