5.2.7.1.2. Sensitivity Analyses

Sensitivity analyses will be performed to assess the robustness of the results generated for the primary efficacy variables.

Analysis of Treatment Policy Estimand

Sensitivity analysis of treatment policy estimand for the co-primary endpoints will be performed using similar analysis method as the primary efficacy analysis. The treatment policy estimand is the difference in means between each fasinumab dose+protocol-defined rescue medication and placebo+protocol-defined rescue medication in the change from baseline to week 16 in the WOMAC pain and physical function scores in the FAS-substudy, regardless of study treatment discontinuation prior to week 16 and regardless of whether or not prohibited medication had been taken. Hence, data from all patients, including data collected after discontinuing treatment up to week 16 will be used in this sensitivity analyses. Missing data for patients discontinued from the study up to week 16 will be imputed assuming the WOMAC scores would on average return to baseline values using the same approach as in Section 5.2.7.1.1.

Tipping Point Analysis

Sensitivity analysis using a tipping point approach with multiple imputation will be performed to assess the robustness of the results due to data that may be missing not-at-random (MNAR).

This approach will introduce a sensitivity parameter, δ , corresponding to a percentage (e.g., 20%, 40%, ..., 100%, 200%, ...) of the treatment effect at each corresponding visit. Estimations will be performed using multiple imputation methodology. Missing data up to week 16 time-point will be imputed 50 times to generate 50 complete datasets by using SAS procedure PROC MI for each δ following the 2 steps below:

- Step 1: The monotone missing pattern is induced by Markov Chain Monte Carlo (MCMC) method in MI procedure using seed number [REDACTED].

- Step 2: The missing data at subsequent visits will be imputed using the regression method for the monotone pattern with seed number [REDACTED] and adjustment for covariates including treatment groups, randomization strata, relevant baseline and values from preceding visits. For missing data due to adverse events or lack of efficacy, δ will be added to the imputed values ($\delta = 0$ corresponds to the MAR assumption).

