5.2.7.2. Analysis of Key Secondary Efficacy Variable(s)

Analyses of continuous variables in key secondary endpoints will use the same analysis method as the primary efficacy variables.

Analysis of categorical variables in key secondary endpoints, the Cochran-Mantel-Haenszel approach stratified by the randomization strata will be used with missing data considered as non-response.

Control for multiplicity for both the primary and key secondary efficacy analyses are described in Section 5.2.7.1.

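### The SAP's Step 3 imputation formula does not centre dropouts at their arm's mean baseline as stated, and its tipping-point rule departs from the protocol without naming an arm or a sign

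*SAP*

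**What the plan says.** **Primary analysis.** SAP 5.2.7.1.1 says missing data after discontinuation for lack of efficacy or adverse events "will be imputed with values centered at the mean baseline value of the treatment group that patients were randomized to". Protocol 9.5.2.1 sets the same target, "imputed with values centered at the mean baseline value of the treatment group that patients were randomized to", and gives no formula. In the SAP, Step 2 imputes under missing at random (MAR), conditioning on arm, strata, baseline and every earlier visit. Step 3 presents its formula as equivalent to the centring: "final imputed score = imputed score under MAR - (mean change from baseline score at the post-baseline time point", that mean being "for the treatment group based on patients on treatment with non-missing data at that time point".

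**Where else it applies.** In the treatment-policy analysis, missing data for patients who left the study "will be imputed assuming the WOMAC scores would on average return to baseline values using the same approach as in Section 5.2.7.1.1". The Patient Global Assessment inherits the method: "Analyses of continuous variables in key secondary endpoints will use the same analysis method as the primary efficacy variables". The 30% responder endpoint does not, because the stratified test "will be used with missing data considered as non-response".

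**Tipping point.** Protocol 9.5.2.1 subtracts k times the treatment effect from the imputed data of fasinumab patients, whatever the dropout reason, until p exceeds 0.05. SAP 5.2.7.1.2 defines delta as a percentage of the treatment effect and adds it under the condition "For missing data due to adverse events or lack of efficacy". It names no arm, lists a shorter set of model terms than the primary MMRM, and offers 0.0167, 0.0333 or 0.05 as thresholds. SAP 1.2.4, which records departures from the protocol's statistical section, lists only endpoint changes.

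**The concern.** Step 3 starts from a value that reflects the dropout's own course and removes the average change of other patients. Someone who leaves for lack of efficacy has usually improved less than those who stay. Subtracting the stayers' larger improvement then puts the imputed score above baseline, which is worse on WOMAC. Prose and formula therefore define different co-primary estimates, and the gap reaches the treatment difference whenever the amount or kind of dropout differs between arms.

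The tipping-point analysis exists to show how adverse the missing data must be before the result fails. Two careful programmers could implement the SAP text differently. Shifting both arms hardly stresses the result when missingness is balanced, and favours fasinumab when placebo has more of it. The sign is also open. A benefit on WOMAC is a negative difference, so adding a signed effect would improve the imputed scores, the opposite of what the analysis is for.

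**Working it through.** **Inputs from the documents.** Effect size 0.46, 200 per arm, 15% dropout at week 16, two-sided 0.0167 (SAP 2.2). No dropout rate by arm or reason, no SD and no visit correlation is given, so those inputs below are assumptions.

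**The plan's own figure.** With 200 × 0.85 = 170 evaluable per arm, SE = √(2/170) = 0.1085 and 0.46/0.1085 = 4.24. The critical value is 2.39, so power is Φ(4.24 − 2.39) = 96.8%. At effect size 0.36 it is 82.3%. Both stated powers reproduce and are not in dispute.

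**Algebra of Step 3.** For one arm and visit, let

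- B = arm mean baseline
- B_D = the dropouts' mean baseline
- M_D = the dropouts' mean MAR-imputed change
- C_O = mean change of on-treatment patients

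The dropouts' mean MAR score is B_D + M_D, so after Step 3 it is B_D + M_D − C_O. Its distance from the stated target is

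(B_D − B) + (M_D − C_O).

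This is zero only if both gaps vanish or cancel. If the target is instead the dropouts' own baseline, the distance is M_D − C_O, which is not generally zero either.

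**Worked case, in SD units.** Large-sample simulation, 400,000 per arm; assumed baseline SD 0.6, visit correlation 0.7, placebo change −0.9, and more lack-of-efficacy dropout on placebo:

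| | Placebo | Fasinumab |
|---|---|---|
| Share missing for adverse event or lack of efficacy | 0.165 | 0.089 |
| C_O | −0.985 | −1.390 |
| M_D | −0.469 | −1.063 |
| M_D − C_O | +0.516 | +0.327 |
| Offset from arm mean baseline | +0.364 | +0.219 |

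The effect on the difference is about 0.165 × 0.364 − 0.089 × 0.219 = 0.060 − 0.019 = 0.041. The fitted estimates agree: −0.500 under Step 3 and −0.459 with exact centring. With completely random dropout both give −0.416.

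**Range, in WOMAC points (0–10).** 150,000 per arm; assumed baseline SD 1.4, change SD 2.2–2.5, visit correlation 0.6–0.8, baseline–change correlation 0 or −0.3, placebo change −2.0; week-16 ANCOVA standing in for the MMRM. Slopes are log-odds of dropout per SD of worse response.

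| Dropout pattern | Step 3 centre minus arm mean baseline |
|---|---|
| Unrelated to response | −0.09 to +0.04 |
| Slope 0.4 | +0.31 to +0.81 |
| Slope 0.8 | +0.67 to +1.66 |
| Slope 1.2 | +0.94 to +2.26 |
| Slope −0.8 (dropouts did better) | −0.68 to −1.57 |
| Baseline severity only, 0.5 per SD | +0.21 to +0.71 |

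These offsets apply only to the imputed subset. The week-16 difference under Step 3, relative to exact centring (slopes 0.4–1.2), is:

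| Placebo / fasinumab dropout for these reasons | Change in the difference |
|---|---|
| 10% / 4% | overstated 2.1–10.9% |
| 6% / 3% | overstated 1.0–5.6% |
| 7% / 7% | within 0.8% |
| 4% / 10% | understated 2.8–12.6% |

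At slope 1.8 the change reaches 14.4%. At trial size (200 per arm, slope 0.8, 300 simulated trials per split, 50 imputations, Rubin's rules):

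| Placebo / fasinumab | Step 3 | Exact centring |
|---|---|---|
| 10% / 4% | −1.26 (SE 0.258, z 4.88) | −1.19 (SE 0.249, z 4.79) |
| 7% / 7% | −1.08 (SE 0.260) | −1.08 (SE 0.251) |
| 4% / 10% | −0.90 (SE 0.263, z 3.43; power 94.7%) | −0.96 (SE 0.253, z 3.78; power 98.0%) |

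**Tipping point.** With shifted fractions f_F and f_P and a shift of k effects,

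z(k) = 0.46[1 − k(f_F − f_P)] / √{[1 + f_F(1 − f_F)(0.46k)²]/200 + [1 + f_P(1 − f_P)(0.46k)²]/200},

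solved for z = 1.96, with f_P = 0 for a fasinumab-only shift and between-imputation variance ignored. Example: f_F = 0.15, k = 3.6 gives 0.2116/0.1084 = 1.95, so the result tips just before 3.6.

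| Rule | Shifted fraction | Tips at k |
|---|---|---|
| Fasinumab only, all missing (protocol) | 15% | 3.6 |
| Fasinumab only, by reason | 10% | 5.2 |
| Fasinumab only, by reason | 5% | 9.7 |
| Fasinumab only, by reason | 4% | 11.7 |
| Both arms, fasinumab / placebo | 10% / 10% | 15.4 (variance alone) |
| Both arms | 10% / 4% | 7.3 |
| Both arms | 4% / 10% | none up to 60 |

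In the last row, k = 1 raises the difference: 0.46 × (1 + 0.06) = 0.49 SD.

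**The case against.** On the primary analysis, Step 3 is one explicit formula applied the same way in each arm, so programmers would not diverge. The surrounding prose is loose, speaking both of the arm's mean baseline and of scores returning to baseline on average, so the intended target can be argued. The large offsets concern the imputed subset under assumed slopes; at trial level the change is small. Exact arm centring also has a cost. If dropout follows baseline severity, it places dropouts 0.60 to 0.71 points below their own baseline, and where fasinumab loses more patients it is less conservative than Step 3.

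On the tipping point, the protocol is the basis for the SAP and names fasinumab patients, so a fasinumab-only worsening shift is the natural reading, and the both-arm figures quantify an unlikely one. Under fasinumab-only rules, z at one full effect of shift is still 3.88, 4.12 or 4.36 for 15%, 10% or 5% shifted. The reason restriction is openly stated and matches the group the primary analysis already treats as not MAR.

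What stands: the sizes rest on assumptions, and the effect on the co-primary test is modest. These points limit the weight of the finding but do not remove it. The formula meets neither reading of the prose. Even on the natural reading, the unlisted reason restriction moves the tipping point from 3.6 to 5.2 or 9.7.

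**Conclusion.** Wrong as written on both counts, and worth fixing. The mismatch between Step 3 and the stated centring is a matter of algebra and needs no assumption. Its size does: near nil when dropout for these reasons is alike in both arms, otherwise about 1% to 13% of the week-16 difference for slopes 0.4–1.2, in either direction. At the design effect the test conclusion is unlikely to change. The responder endpoint is untouched, and the treatment-policy analysis is less exposed because it uses observed off-treatment data.

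The tipping-point text has the larger practical consequence. Arm and sign are unstated, and the dropout-reason restriction departs from the protocol without appearing in SAP 1.2.4. Depending on the reading, the reported tipping point ranges from 3.6 effects to none at all. Confidence is high on the text and lower on the magnitudes.

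**What to change.** **Step 3.** For each arm and visit, replace the subtracted term with one constant: the mean MAR-imputed score of that arm's dropouts for these two reasons, averaged over the 50 imputations, minus that arm's mean baseline. This gives the stated centre exactly and keeps the between-imputation variance. Drawing directly around the arm's mean baseline would also do. If the intended target is zero mean change from the dropouts' own baseline, reword the text and subtract the dropouts' own mean MAR change. If the present formula is intended, correct the prose to describe it. Use the same rule for the Patient Global Assessment and the treatment-policy analysis.

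**Tipping point.** State that delta is +k times the absolute treatment effect (a worsening on WOMAC) and applies to fasinumab patients only. Apply it to all their imputed data, as in the protocol, or keep the reason restriction and list and justify it in SAP 1.2.4. Use the primary MMRM terms and judge at 0.05.

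**Cost.** A few SAP sentences and small program edits; the estimate may move slightly in either direction. SAP section 1 requires the final plan before the first-step lock. Sub-study enrolment ended on 7 February 2018, so the last week-16 visits fell around June 2018. If that lock has passed, keep the specified analyses and report the corrected ones as labelled supplementary analyses.

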5.2.7.1.2. Sensitivity Analyses

Sensitivity analyses will be performed to assess the robustness of the results generated for the primary efficacy variables.

Analysis of Treatment Policy Estimand

Sensitivity analysis of treatment policy estimand for the co-primary endpoints will be performed using similar analysis method as the primary efficacy analysis. The treatment policy estimand is the difference in means between each fasinumab dose+protocol-defined rescue medication and placebo+protocol-defined rescue medication in the change from baseline to week 16 in the WOMAC pain and physical function scores in the FAS-substudy, regardless of study treatment discontinuation prior to week 16 and regardless of whether or not prohibited medication had been taken. Hence, data from all patients, including data collected after discontinuing treatment up to week 16 will be used in this sensitivity analyses. Missing data for patients discontinued from the study up to week 16 will be imputed assuming the WOMAC scores would on average return to baseline values using the same approach as in Section 5.2.7.1.1.

Tipping Point Analysis

Sensitivity analysis using a tipping point approach with multiple imputation will be performed to assess the robustness of the results due to data that may be missing not-at-random (MNAR).

This approach will introduce a sensitivity parameter, δ , corresponding to a percentage (e.g., 20%, 40%, ..., 100%, 200%, ...) of the treatment effect at each corresponding visit. Estimations will be performed using multiple imputation methodology. Missing data up to week 16 time-point will be imputed 50 times to generate 50 complete datasets by using SAS procedure PROC MI for each δ following the 2 steps below:

- Step 1: The monotone missing pattern is induced by Markov Chain Monte Carlo (MCMC) method in MI procedure using seed number [REDACTED].

- Step 2: The missing data at subsequent visits will be imputed using the regression method for the monotone pattern with seed number [REDACTED] and adjustment for covariates including treatment groups, randomization strata, relevant baseline and values from preceding visits. For missing data due to adverse events or lack of efficacy, δ will be added to the imputed values ($\delta = 0$ corresponds to the MAR assumption).

Each imputed data set will be analyzed using the MMRM model with treatment, randomization strata, and relevant baseline included in the model. For each δ the SAS MIANALYZE procedure will be used to generate valid statistical inferences by combining results from the 50 analyses using Rubin's formula. By progressively increasing δ , the sensitivity analysis will explore the tipping points, e.g., δ value when the p-value for a treatment comparison is above 0.0167, 0.0333 or 0.05. Results will be then summarized using summary tables and graphs.

Per Protocol Set Analysis

Sensitivity analyses based on the PPS will be performed using the MMRM approach.

Subgroup Analysis

Descriptive analyses will be performed on the primary endpoints and key secondary endpoint of PGA to summarize the treatment effects across subpopulations defined by baseline randomization strata (index joint and K-L score category), demographics (age group, sex, race) and baseline characteristics (weight and BMI categories). Subgroup analysis based on other medical conditions may also be performed. Forest plots for the subgroup analysis will be provided.

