Additional sensitivity analysis using tipping point approach with multiple imputation will be performed to assess the robustness of the results due to data that may be missing not-at-random (MNAR). Multiple imputation will be based on monotone missing data structure of the change from baseline score using regression option in PROC MI. Monotone missing data structure will be achieved using MCMC option of PROC MI. After each imputation, a fasinumab patient's imputed data will subtract k (e.g., 20%, 40%, 100%, ...) times the treatment effect at each corresponding time point. By progressively increasing coefficient k, the sensitivity analysis will explore the tipping point, ie, the upper bound on the critical value of coefficient k at which conclusion from the primary analysis will be overturned ( $p > 0.05$ ). Additional sensitivity analyses will be performed the same way for the primary and selected secondary endpoints using the PPS.

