5.2.7.3. Analysis of Additional Secondary Efficacy Variable(s)

Analyses of continuous variables in other secondary endpoints will use the same analysis method as the primary efficacy variables.

No control for multiplicity will be made for these analyses. Tests for comparing each fasinumab dose versus placebo will utilize a nominal 2-sided alpha level of 0.05.

NRS

For the analysis of average weekly walking index joint pain using the NRS pain scale, baseline is defined as the average of the non-missing values during 7 days prior to taking study drug. For each week, the average of the non-missing values during the 7 days on or prior to that week will be used. If all values are missing for the 7 days, the value for that week is set to missing.

The MMRM model will be used for the analysis with terms for the randomization strata (K-L category [2-3 vs. 4] and index joint [hip or knee], geographic region), treatment, week treatment-by-week interaction as fixed effects, and baseline NRS value as a covariate. The least-squares (LS) means for the mean change from baseline to each week as well as the LS mean differences between fasinumab doses and placebo, with their corresponding standard errors (SEs), p-values and associated 95% confidence intervals, will be provided from the MMRM. If the model does not converge using unstructured covariance matrix, ARH(1) covariance structure will be used.

Responder analyses

The percentage of patients who are responders based on WOMAC pain and physical function subscale scores and Patient Global Assessment scale scores defined by at least a 30% reduction and at least a 50% reduction from baseline to each post-baseline week will be summarized and plotted by the treatment group. The percentage of patients who are responders based on the Osteoarthritis Research Society International Standing Committee for Clinical Trials Response Criteria Initiative and The Outcome Measure in Rheumatology (OMERACT-OARSI) responder criteria ([Appendix 11.3](#)) will be summarized and plotted by the treatment group. Cochran-Mantel-Haenszel (CMH) test, stratified by the randomization strata will be applied for the responder analysis. Missing data is considered as non-response in this analysis.

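### The SAP's tipping-point step adds an unsigned share of the treatment effect with no arm named, where the protocol subtracts it from fasinumab patients; as worded it need not stress the co-primary result

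*SAP*

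**What the plan says.** Protocol 9.5.2.1 describes the shift this way: after each imputation "a fasinumab patient's imputed data will subtract k" times the treatment effect at the matching time point, with k of 20%, 40%, 100% and so on. Only fasinumab patients are shifted, and the sentence covers their imputed data without regard to the reason for missingness.

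SAP 5.2.7.1.2 uses a sensitivity parameter δ, set as a percentage "of the treatment effect at each corresponding visit". Step 2 reads: "For missing data due to adverse events or lack of efficacy", δ "will be added to the imputed values", and δ = 0 is the missing-at-random case. By raising δ step by step, "the sensitivity analysis will explore the tipping points", with thresholds of 0.0167, 0.0333 and 0.05. The SAP does not say whether the treatment effect inside δ is signed or a magnitude, and it does not limit the shift to an arm.

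Two other places fix the scale. SAP 11.3 puts the WOMAC pain and function scores on 0 to 10. SAP 5.2.7.3 defines responders by "at least a 30% reduction and at least a 50% reduction from baseline", so a lower score is better. SAP 5.2.7.1.1 reports the least-squares mean changes "as well as the difference of the estimates between fasinumab and placebo". SAP 1.2.4, which lists departures from the protocol's statistical section, does not mention the tipping-point analysis.

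**The concern.** A tipping-point analysis is meant to show how much worse than missing-at-random the fasinumab dropouts would have to be before the conclusion is lost. It does this only if the shift worsens the imputed fasinumab scores relative to placebo.

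The two documents apply opposite operators to a quantity that both tie to the treatment effect. Under any single sign convention, one of them moves the dropouts the wrong way. With a signed fasinumab-minus-placebo effect, it is the SAP. A programmer who takes the estimated difference from the primary model, multiplies it by the listed percentages and adds it as Step 2 says would be improving the scores of fasinumab patients who left for adverse events or lack of efficacy. The output would then look robust whatever the true behaviour of those patients. The missing arm restriction is a second, separate way for the analysis to lose its force.

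**Working it through.** **The plan's own figure first.** The documents give no tipping-point figure, so the check starts from the power statement in SAP 2.2 and protocol 9.2: 200 per arm, 15% dropout, two-sided 0.0167. Evaluable per arm = 200 × 0.85 = 170. The standard error in SD units is √(2/170) = 0.1085. For an effect of 0.46, z = 0.46/0.1085 = 4.24 and power is 96.8% by the normal approximation (96.6% by noncentral t), against the stated 96%. For 0.36, power is 82.3% (81.9% by t), against 82%. Both reproduce.

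**Shifted estimate.** Let TE = -0.46 SD (fasinumab minus placebo). Let pF and pP be the shares of each arm that are shifted, and sF and sP the shifts in SD.

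- Difference: D = TE + pF·sF − pP·sP
- Variance: Σ over arms of [1 + p(1−p)s²]/170
- Tip: the smallest k at which two-sided p exceeds 0.05

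The documents do not give pF or pP. They are assumptions, ranged from 1% to 15%; 15% corresponds to all planned dropout being for adverse events or lack of efficacy.

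**Worked case, fasinumab only, pF = 10%.**

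- Protocol operator (subtract a negative effect): D = -0.46 + 0.10 × 0.46k, so -0.414 at 100% and -0.368 at 200%.
- SAP operator with signed δ (add a negative effect): D = -0.46 − 0.10 × 0.46k, so -0.506 at 100% and -0.552 at 200%. |z| rises from 4.24 to 4.64 and 4.99.

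**All readings.**

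| Reading of the shift | Shares assumed | Tips at k of about |
|---|---|---|
| Protocol; equally, SAP with positive δ in fasinumab only | pF 15% / 10% / 5% | 336% / 489% / 903% |
| SAP, signed δ, fasinumab only | pF 15% / 10% / 5% | no tip up to 20,000% |
| SAP, signed δ, fasinumab only | pF 1% | 19,400%, from variance growth alone |
| SAP, signed δ, both arms | pF 5%, pP 10% | 753% |
| SAP, signed δ, both arms | pF 5%, pP 15% | 457% |
| SAP, positive δ, both arms | pF = pP = 10% | D stays at -0.46; 1,391%, from variance growth alone |
| SAP, positive δ, both arms | pF = pP = 7.5% | D stays at -0.46; 1,584%, from variance growth alone |
| SAP, positive δ, both arms | pF 5%, pP 10% | D moves away from zero; no practical tip (about 17,200%) |
| SAP, positive δ, both arms | pF 10%, pP 5% | 753% |

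Only a worsening shift confined to fasinumab moves D toward zero in every case. When both arms are shifted, the result turns on which arm lost more patients to adverse events or lack of efficacy. These values are analytic illustrations with 170 effective patients per arm, not output from the planned imputation and repeated-measures model.

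**The case against.** The strongest reply is that the SAP never calls δ negative. It starts δ at zero and increases it, which fits a positive quantity. A positive δ added to a higher-is-worse score makes the dropout worse, in agreement with the protocol's subtraction of k times a negative effect. The primary estimand, "The estimand for the primary efficacy objective is the difference in means between each fasinumab dose+protocol-defined rescue medication and placebo+protocol-defined rescue medication", does not state an order of subtraction. Step 3 of the primary imputation does subtract a signed mean change to move scores back up, but there the quantity is named and the formula written out, so it is weak evidence about δ. All of this stands: a reading exists in which the SAP's direction is correct.

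A reader might go further the other way and infer that the SAP has reversed the rule, so that a significant result can never tip. The documents do not support that. The negative sign is an inference. The claim also needs the shift confined to fasinumab, a restriction found in the protocol and not in the SAP. With signed δ in both arms and more of these dropouts on placebo, the analysis tips at about 457% to 753%.

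It is also fair that this is one sensitivity analysis among several. The primary analysis already returns adverse-event and lack-of-efficacy dropouts to baseline on average, and treatment-policy and per-protocol analyses are planned. A difference drifting away from zero would probably be noticed in the planned tables and graphs.

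The reply does not rescue the wording. The favourable reading requires the treatment effect to be a magnitude in the SAP and signed in the protocol, and neither document says so. It also leaves the arm open, so even a correctly directed δ may leave the difference where it was.

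**Conclusion.** The conflict between SAP 5.2.7.1.2 Step 2 and protocol 9.5.2.1 is real and covers three things: operator, arm, and which missing data are shifted. It is an ambiguity that can run the stress test backwards, not proof that the sponsor intends to do so.

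Its size depends on the reading. With signed δ applied to fasinumab patients, there is no tip at any practical percentage, against about 336% to 903% under the protocol's rule for shares of 15% down to 5%. With positive δ added to both arms in equal shares, the difference does not move at all. The figures rest on the plan's effect of 0.46 SD and 15% dropout, on assumed dropout shares, and on a two-sided 0.05 threshold.

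The primary test, the error control and the stated power are untouched. What is at stake is whether the robustness statement for the co-primary endpoints means anything. It should be corrected before the first-step database lock.

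**What to change.** In SAP 5.2.7.1.2 Step 2:

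1. Define δ = −k × (fasinumab minus placebo least-squares mean difference in change from baseline at that visit), so that for a beneficial effect δ > 0 means a worse imputed score.
2. State that δ is added to imputed scores in the fasinumab arms only, as in the protocol.
3. Reconcile which missing data are shifted: the protocol's wording covers a fasinumab patient's imputed data, the SAP's only data missing for adverse events or lack of efficacy. If the narrower scope is meant, list it in SAP 1.2.4 as a departure.
4. Add a program check that the estimated difference moves toward zero as k increases.

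The cost is a few sentences of SAP text and one programming check. No new data are needed. The reported robustness may be less favourable than under the signed or both-arm readings.
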